fMRI studies indicate that individuals with autistic symptoms exhibit reduced responsiveness to affective touch in the orbitofrontal cortex (OFC) and superior temporal sulcus (STS), and individuals with diagnoses of ASD show reduced activity in these regions as well as in the bilateral insula and other regions involved in social and emotional processing (Voos et al. 2012, Kaiser et al. 2015). To understand the mechanism by which MDMA increases reactivity to affective touch, we will use functional magnetic resonance imaging to test the effects of the drug on BOLD responses to affective touch in individuals with a range of autistic traits. We hypothesize that individuals with high scores on the ASQ will exhibit reduced OFC, STS, and insular responses to affective touch, and that MDMA will enhance touch-related activity in these regions, correcting these deficits.

**Specific Aim 3: To determine the mediating role of oxytocin in the effects of MDMA on responses to affective touch in individuals with a range of autistic traits**

MDMA has been shown to increase plasma oxytocin, raising the possibility that oxytocin mediates the enhancement of social behavior induced by MDMA. Here we propose to assess whether the MDMA-induced rise in plasma oxytocin predicts enhanced responses to affective touch.

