### **Study Tasks:**

#### Affective Touch Task

This task will be administered while subjects are in the scanner. In this task, touch will be administered using a 5 cm wide goat hair brush applied to a 9cm section of the forearm. Brush will be used rather than hand touching (i.e. skin-to-skin contact) to control for variation in skin temperature (Ackerley et al, 2014). We will use a hand-held brush, as previous reports indicate no difference in ratings of tactile stimulation delivered manually versus a force-controlled robot (Triscoli et al, 2013). Participants will be instructed to look straight ahead at a fixation cross presented on the screen throughout the brushing trials to avoid providing any visual cues regarding touch administration. The experimenter will wear headphones to receive metronomic audio cues for consistency in brushing velocity. The task consists of four blocks of 8 trials each, four at each velocity, 3 cm/s ("slow") and 30 cm/s ("fast"), with velocity order within each block pseudorandomized but not repeated more than 3 times. Ratings of "pleasantness," "intensity," and "desire to experience that type of touch again," will be conducted during intertrial intervals using a 7-point Likert scale ranging from 1 (i.e. extremely unpleasant) to 7 (i.e. extremely pleasant). A 1-2 sec variable inter-trial interval (ITI) will separate each rating, with the

final rating followed by a 7- 9 sec variable ITI before the next trial begins. The primary behavioral ratings in this task are the ratings of pleasantness of the brushing.

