### **Data Analysis**

Subjects will be grouped according to ASQ scores in three groups; low (0-10), medium (10-20), and high (20-32), which will be used as a between-subjects factor in the analysis. The subjective and mood effects of the drug will be assessed using a repeated measures analysis of variance (ANOVA) with AQ (low, medium, high) as a between-subjects factor, and dose (placebo or MDMA) and time as within-subjects factors. Imaging data will be compared within subjects across MDMA and placebo conditions. For data pre-processing we will combine realignment algorithms (MCFLIRT), locally written code, and normalization procedures from Statistical Parametric Mapping software (SPM8; Wellcome Trust Center for Neuroimaging, London). Strict quality control procedures will be in place to evaluate movement (excluding subjects > 2mm translation, and 1 degrees rotation in re-alignment parameters) and ensure proper normalization to the MNI152 template. Functional data will be processed and analyzed using conventional methods implemented with SPM8, previously described in our papers (Gorka et al., 2013; Wardle et al., 2014a). Statistical analysis will use the general framework of the modified General Linear Model implemented in SPM8 in combination with a temporal convolution model for event-related analyses in a random effects model. Statistical inference will use random field theory to account for non-independent observations within a smooth map, providing corrected probabilities. Given hypotheses about specific brain regions, small volume corrections will be applied to provide appropriate levels of stringent controls to hypothesis testing. We will implement 2 complementary approaches to test regional activation: 1) hypothesis-driven anatomically-focused region of interest (ROI)-based analysis of the primary contrast of interest; and 2) whole-brain voxel-wise 'search' of activation not constrained to ROIs related to these same factors. We will use repeated-measures ANOVAs to assess significant effects of drug (placebo versus MDMA) on each of the two brush velocities for the touch task (slow vs. fast) and the social interaction task (self vs. other). Change scores will be computed for ratings of pleasantness of affective touch (MDMA-placebo). Oxytocin levels and subjective ratings will be compared with ANOVAs with ASQ (low, medium, high) as a between-subjects factor, and dose (placebo or MDMA) as a within subjects factor.

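### Aim 3 has no analysis linking oxytocin to touch response: the planned ASQ-by-dose ANOVAs treat each outcome separately and cannot show that a larger oxytocin rise predicts a larger response

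*Combined protocol and SAP*

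**What the plan says.** The title of Specific Aim 3 is "To determine the mediating role of oxytocin in the effects of MDMA on responses to affective touch" in people with a range of autistic traits. Its text narrows this to a question about individuals: "Here we propose to assess whether the MDMA-induced rise in plasma oxytocin predicts enhanced responses to affective touch".

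The Data Analysis section says of oxytocin only: "Oxytocin levels and subjective ratings will be compared with ANOVAs with ASQ (low, medium, high) as a between-subjects factor, and dose (placebo or MDMA", "and dose (placebo or MDMA) as a within subjects factor". The sentence before it reads "Change scores will be computed for ratings of pleasantness of affective touch (MDMA-placebo" but attaches no test to the score. No oxytocin change score is defined. No correlation, regression, covariate or mediation model joining oxytocin to ratings or to BOLD response appears in that section or elsewhere.

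The Affective Touch Task section sets up slow (3 cm/s) and fast (30 cm/s) brushing: "The task consists of four blocks of 8 trials each, four at each velocity". It adds: "The primary behavioral ratings in this task are the ratings of pleasantness of the brushing". No velocity is named there. Data Analysis tests drug effects "on each of the two brush velocities for the touch task (slow vs. fast", but does not say which velocity the pleasantness change score uses.

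Under Neuroendocrine measures, saliva and plasma oxytocin are taken 120 minutes after the capsule. No pre-dose sample is stated, so the rise can only mean the MDMA session minus the placebo session.

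**The concern.** Aim 3 asks whether people whose oxytocin rises more also respond more to touch. Answering it requires each participant's oxytocin change to be matched with the same participant's touch change. The planned ANOVAs never do this. One is run on oxytocin and one on ratings.

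If the plan is followed as written, the evidence on Aim 3 is two parallel drug effects, each broken down by ASQ group. Two outcomes can both move under a drug with no relation between them across individuals, so that evidence cannot support a predictive or mediating role. If the link is tested later without a prior definition, the velocity, specimen and covariates would all be chosen after the data are known, which weakens any positive finding.

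**Working it through.** **1. The plan's own power figure.** Inputs from Subjects: d = 0.44 for the MDMA effect on touch pleasantness, N = 45, power above 80%. Alpha and sidedness are not stated, so two-sided 0.05 is assumed, and d is taken as a paired difference. The noncentrality is 0.44 × √45 = 2.95 on 44 df. Power is 82.3% (89.6% one-sided), and the smallest N giving 80% two-sided is 43. The stated figure reproduces, but it concerns the drug effect on pleasantness and says nothing about an oxytocin–touch association.

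**2. What the ANOVAs can see.** With two dose levels, the dose effect and the ASQ-by-dose interaction depend only on the within-person differences of one outcome: their group means and their spread. Which oxytocin difference sits beside which touch difference does not enter. A constructed data set (45 people, three groups of 15) shows this. The same values were paired in two ways within ASQ groups:

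| Quantity | Pairing A | Pairing B |
|---|---|---|
| Oxytocin: F for mean change | 46.45 | 46.45 |
| Oxytocin: F for group difference in change | 0.45 | 0.45 |
| Touch: F for mean change | 10.76 | 10.76 |
| Touch: F for group difference in change | 0.07 | 0.07 |
| Correlation of the two changes | +0.91 | −0.91 |

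Every ANOVA statistic is identical, while the answer to Aim 3 reverses.

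**3. What a direct test could detect.** Fisher's z, two-sided 0.05 (assumed), n complete pairs, k covariate terms. The standard error of z is 1/√(n − 3 − k), and the r detectable with 80% power is tanh(2.802/√(n − 3 − k)).

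- n = 45, k = 0: tanh(2.802/√42) = 0.407
- n = 45, k = 2 (ASQ score, session order): tanh(2.802/√40) = 0.416
- n = 45, k = 3 (three ASQ groups, session order): tanh(2.802/√39) = 0.421
- n = 40, k = 2: tanh(2.802/√35) = 0.44
- n = 35, k = 2: tanh(2.802/√30) = 0.47

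Power at n = 45, k = 2 is 25%, 50% and 76% for r = 0.2, 0.3 and 0.4. With k = 3 it is 24%, 49% and 75%. If the observed r were 0, the 95% interval with k = 2 would be ± tanh(1.96/√40) = ±0.30. The documents give no expected r; 40 and 35 pairs are assumed values.

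**4. Sampling time and specimen.** The capsule is given at 9:30, and 9:30 + 120 minutes = 11:30. The Timeline places the scan at 11:00–11:45, so 11:30 falls inside it. The Study Sessions paragraph has participants taken to the scanner at 10:30 for a scan of about 45 minutes. A scan starting at once would end at 11:15, before the sample. The Timeline lists no oxytocin sample. The Measures paragraph under Drugs names saliva only, while Aim 3 and Neuroendocrine measures name plasma.

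**The case against.** The best counter-reading is that the change-score sentence, placed just before the oxytocin sentence, implies that the two will be correlated. That may be the intent, but no test is stated, no oxytocin change is defined and no velocity is chosen. The oxytocin sentence itself describes group-by-dose comparisons only.

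It can also be said that the ANOVA does necessary work. This stands: it tests whether MDMA raises oxytocin and whether the rise differs by ASQ group. Matching patterns across three group means would still be only group-level evidence, not prediction for individuals.

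A regression gives an association, whereas the Aim 3 heading speaks of mediation. This also stands, so the wording of the aim's conclusion has to change with the analysis. Session order and a continuous ASQ score are not in the planned models; keeping the three groups instead changes the detectable r only from 0.416 to 0.421.

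Two stronger readings are tempting and are not supported:

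- A reader might infer a markedly inflated false-positive rate because the velocity is open. Testing slow, fast and slow-minus-fast without adjustment would give 11–12%, and slow and fast alone 7–9% (slow–fast correlation assumed 0 to 0.9). The plan proposes no such set of oxytocin tests, so these figures are not evidence of harm.
- A reader might infer that plasma will not be collected, or that sampling certainly collides with the scan. Aim 3 and Neuroendocrine measures both name plasma. The Measures paragraph is a summary that also omits the cortisol sample. The Timeline is not exhaustive, since it also omits the TOSCA and the End of Session Questionnaire. Whether 11:30 falls inside the scan depends on which section is followed.

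**Conclusion.** The concern holds for the analysis: the stated oxytocin analysis does not fit Aim 3 and, followed as written, cannot answer it. This follows from the structure of the ANOVA and rests on no assumed effect size. It should be fixed before unblinded data are examined. Aims 1 and 2 and the stated sample size are not affected.

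The limit on what a proper test can deliver does rest on assumptions: two-sided 0.05, Fisher's approximation and complete pairs. The detectable |r| of about 0.42 is the best case, because it needs all 45 participants to have oxytocin and ratings in both sessions. The scan-time and specimen discrepancies are a separate, minor matter of reconciliation.

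**What to change.** In Data Analysis, add one prespecified test for Aim 3:

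- **Outcome:** slow-touch (3 cm/s) pleasantness change, MDMA minus placebo.
- **Predictor:** plasma oxytocin difference, MDMA minus placebo.
- **Adjustment:** ASQ (score, or the three planned groups, stated in advance) and session order.
- **Report:** the slope with its 95% confidence interval.

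Reword the Aim 3 conclusion as an association. Label any mediation, saliva, fast-touch or neural analysis exploratory. State the detectable |r| (about 0.42, 0.44 and 0.47 for 45, 40 and 35 complete pairs), so that a null result is not read as no relation.

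Separately, reconcile Study Sessions, Timeline, the Measures paragraph and Neuroendocrine measures on scan start, sampling time and specimen. State whether the sample precedes or follows the touch ratings, and keep this the same in both sessions.

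The cost is a few sentences and one extra regression with limited power. No further samples are needed if plasma is collected as Aim 3 and Neuroendocrine measures say. If it is not, Aim 3 must be restated for saliva or plasma sampling added.

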### **Human Subjects Information**

**Recruiting methods:** We will place print ads in newspapers and on online job search sites such as craigslist.org, and flyer in the Chicago area. Healthy volunteers who respond to our ads are screened using our standard screening protocol for all studies in the Human Behavioral Psychopharmacology Laboratory, which is separately approved by the IRB under Protocol #13681B

**Obtaining consent:** Written informed consent for the screening session only is obtained at the screening according to procedures outlined in Protocol #13681B. Written informed consent for the study procedures is obtained at the orientation session, after a verbal explanation of study procedures, check of comprehension, and an opportunity for the participant to ask any questions they may have. Consent is verbally re-verified at the beginning of each study session.

**Risk to subjects:**

**1. Diagnostic procedures and questionnaires:** Some of the questions asked during the screening may be considered sensitive information, including drug use history and psychiatric history. We have rigorous procedures in place to ensure confidentiality of data, including locked cabinets for confidential files, subject coding, secure computer systems, and rigorous training of personnel. Please see screening protocol #13681B for full information on steps taken to protect information gathered as part of the screening.

**2. Study drugs:**

Common side effects of MDMA include increased heart rate and blood pressure; bruxism; mydriasis; mild sensory and perceptual impairment; dryness of the mouth; difficulty concentrating; nausea; confusion; shakiness or tremor; changes in appetite; anxiety or panic attacks; and insomnia. We have used similar doses of MDMA in previous studies without adverse reactions (Bedi et al, 2009). The side effects of methamphetamine are similar, including increases in heart rate or blood pressure, dizziness, restlessness, tenseness, anxiety, nervousness, headache, diarrhea, sweating, constipation, difficulty sleeping, and dry mouth. These doses are unlikely to cause adverse effects in participants such as ours who are carefully screened for psychiatric and medical problems, and who report having used ecstasy previously without adverse effects. Participants will be monitored during experimental sessions for any symptoms of adverse effects, and a physician will be on call during and after sessions. To reduce the risk of hyperthermia sometimes associated with recreational use of ecstasy, we will keep room temperature low and provide subjects with water during study sessions. To prevent risk of hyponatremia due to excessive water intake, we will monitor water consumption during sessions, and participants will be restricted to consuming no more than one pint of water per hour after capsule administration and weighed to ensure that they are not retaining excessive fluids. Given these precautions, and the absence of evidence of the development of these conditions as a result of MDMA administration in controlled settings, we believe that administration of MDMA in the context of this study poses a low risk to participants. The doses selected for this study have been given to subjects in at least 29 previous studies, and no serious adverse effects were reported with these and even higher doses of MDMA (for review see Dumont and Verkes, 2006). Chronic use, or high doses of MDMA, have been shown to cause damage to brain cells in laboratory animals. However, this is unlikely at the doses subjects will receive in this study (see Vollenweider et al., 1999). Although any exposure to drugs with potential for abuse may entail some risk for development of problems of abuse, this is extremely unlikely in view of the low doses and limited number of drug exposures, the careful screening of subjects, and the laboratory setting in which studies are conducted. Subjects will receive

only two controlled, low to moderate doses of MDMA, and these doses will be separated by at least 72 hours. There is little evidence that administration of a drug in a medical setting (for medical or research purposes) increases the susceptibility to abuse the drug in non-medical settings (Bigelow et al., 1995; College on Problems of Drug Dependence, 1995; Kaufman et al., 2000; Schuster, 1989). A recent study assessing substance use and psychosocial outcomes in participants who were administered repeated doses of marijuana, methamphetamine or zolpidem as part of a laboratory research study concluded that there was no evidence of any alteration to psychosocial functioning or drug use as a result of participation in the study (Vadhan et al., 2006). Thus, we believe that it is very unlikely that subjects exposed to these drugs in our medical/laboratory setting after careful screening will increase their use as a result of participation.

3. fMRI procedure:

fMRI is a non-invasive procedure that is widely used and safe. Potential risks such as static magnetic field, radio-frequency field, magnetic field gradients, and acoustic noise are rarely dangerous or life-threatening. The risks of the study are extremely small when exclusion criteria are observed and are outweighed by the large benefits of these studies to clinical and neuroscience research. Subjects will be asked questions about claustrophobia and the presence of metal in their body to make sure that the MRI scan is safe. If they have implanted metal of any kind, they will not be scanned. For their safety they will be asked to remove any metal in their clothing before the scan (for example, belts and rings). Subjects will be given noise dampening head phones to reduce the discomfort due to the noise of the machine. Subjects are asked to report any discomfort immediately. They may discontinue the scan at any time if they are too anxious to continue, by communicating with the scanning operator that they would like to end the session. Additional minor or rare risks include: i) discomfort from lying still for 30 min-1 hour; ii) fast imaging sequences may potentially induce peripheral nerve stimulation (PNS) that may cause mild discomfort but is not harmful to participants; iii) anxiety or panic attack caused by close confinement in the scanner; iv) the MRI may reveal a minor or significant lesion in the brain (e.g., tumor) previously unknown to the subject. The CRC nurse and PI and also a Board-certified psychiatrist will be available and/or present during the fMRI scans in order to evaluate the emergence of any anxiety/panic attack, elevated levels of anxiety, or emotional discomfort during the procedure.

**Benefits to subjects:** There is no direct benefit to the participants. We hope that the information learned from this study will contribute to our knowledge of factors influencing drug use. Additionally, participating in research may be an educational experience for participants, and we attempt to facilitate this by providing a thorough debriefing including an explanation of study hypotheses and procedures at the conclusion of participation.

**Subject time commitment and compensation:** The orientation typically takes approximately one hour. The two study sessions are estimated to last 4.5 hours each, for a total of 10 hours spent in study sessions. Participants are compensated \$10 for the orientation session and \$40 for each study session, with a bonus of \$60 for completion of all study sessions, giving a total of \$150.

**Data and Safety Monitoring:** The PI will monitor data collection and safety at weekly staff meetings. During these meetings, the PI will review and respond appropriately to (1) data collection and storage practices and (2) any adverse or unexpected effects from the study drugs. Both the study physician and PI will monitor the safety of study participants on an ongoing basis. The physician connected with this study will be on call during the experimental

sessions and for 24 hours after sessions. Subjects will be given telephone numbers for the study physician and investigators in case they experience unpleasant effects after leaving the laboratory. If a serious or unexpected adverse event were to occur, the staff member most closely involved with the subject at that time or the physician would notify the PI immediately. The PI would then take appropriate action and communicate with all necessary offices within the University and the FDA.
